6.2 Secondary Outcomes

Self-reported patient satisfaction on overall appearance, size, and color, will be recorded and examined using Chi-Square across drug for the final visit. Application frequency and safety may also be evaluated.

A cross-sectional analysis of sociodemographic data and self-reported DSAP-related impact on QoL (scale 1-10) was averaged at baseline, while the RAND36 and Dermatology Life Quality Index (DLQI) were distributed and averaged at weeks 0, 4, 8, and 12. Statistical measures used in analysis included a Repeated Measures Analyses of Variance (ANOVA) and Pearson correlation coefficient.

7. Missing Data

Patients who failed to submit photographs for the analysis will be removed from the DSAP-GASI efficacy analysis. Missing data will be recorded and excluded from analysis.

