4.0 Study Endpoints

- Percentage of clearance of disseminated superficial actinic porokeratosis lesions after 12 weeks of therapy
- Validated scale changes: Patient Quality of Life (RAND36, DLQI), Physician Global Assessment Scale (DSAP-PGA), Actinic Keratosis Field Assessment Scale
- Clearance of coronoid lamella on dermoscopy (or photograph) after 12 weeks of therapy.

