6.2 Secondary outcomes	
7. Missing data	

1 Introduction

The aim of this study is to test in a single-center randomized clinical trial, if topical statins combined with topical cholesterol can reduce the severity (size, color, quality of life impact) of disseminated superficial actinic vs statin therapy alone.

This statistical analysis plan (SAP) will give more detailed descriptions of the endpoints in the study and the corresponding analysis.

2 Study Design

Patients with previous diagnosis of DSAP will be approached for informed consent as directed in sections 8.0 and 9.0 of the protocol. If the patient is eligible for the study, he or she will be randomly assigned to one of two groups, Group A (cholesterol/lovastatin) and Group B (lovastatin only). The patient will not be informed of which group they are in and will not be informed of what their study medication is, allowing single-blinding. Researchers will not be masked.

Enrolled subjects will be followed up at monthly intervals for three months via virtual check-in using an MUSC approved HIPAA compliant technology. At each visit, participants will undergo brief, limited physical examination (in order to determine disease severity and affected body surface area); additionally, clinical photographs of the lesion will be obtained in clinic or shared virtually with the investigators via secure email (sent to MUSC Outlook email). The physical exam will occur in-person or by using the virtual visit technology, which allows us to see the patient and visualize their skin findings. Photographs will be stored in the coded study-specific medical record for further analysis of lesion features.

At each visit a Patient Quality of Life, Physician Global Assessment Scale, and RAND36 will be administered.

Patients will be contacted via formal virtual visits at weeks 4, 8, and 12 and non-formal check-ins at weeks 2 and 6. Patients will be asked about compliance and any adverse effects experienced. Patients are also encouraged to contact [name] and/or [name] at any given point during the study if they think they are experiencing study-related side effects. Immediate consultation will follow to determine the severity of such event and necessary impacts on patient health and participation. Non-formal check-ins will be done over phone by study team member to assess for any adverse effects at weeks 2 and 6 of treatment.

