2.1 Sample Size Calculation

DSAP is a rare disease that effects people from a wide geographical region. The goal sample size for the study was to recruit 50 subjects, however, due to recruiting limitations and state regulations, we were only able to enroll 31 patients. No formal sample size calculation was necessary as this study is first of its kind.

3. Aims and Objectives

• The purpose of this study is to evaluate the effectiveness of cholesterol/lovastatin versus lovastatin alone to treat porokeratosis. Our working hypothesis is that both topical cholesterol/lovastatin and lovastatin alone are helpful in treating patients with disseminated superficial actinic porokeratosis (DSAP).

DSAP: Single-Blinded randomized trial

Aims:

- 1. To evaluate the response (lesion size, color, patient quality of life) to treatment with topical cholesterol/lovastatin and lovastatin alone in a series of patients with the diagnosis of DSAP.
- 2. To characterize lesion patterns following topical treatment and patterns of lesion regression.
- 3. Access quality of life outcomes through RAND36 and DLQI surveys.

4. Outcomes

This section will present the outcomes investigated to answer the study aims and objectives. The analyses are described in section 6 Analyses.

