6.1 Primary outcome

The primary analysis will compare the improvement in DSAP-GASI scores before treatment and after treatment in both groups. Only participants with clearly documented photos across all visits will be considered for the DSAP-GASI efficacy analysis. The scores will be graded by two blinded, trained physicians. Cronbach's Interrater reliability will be calculated among raters across visits and the scores will be averaged for each of the four visits. Overall efficacy will be examined using a 2X4 (Drug X Time) Repeated Measures Analyses of Variance (ANOVA). The statin/cholesterol vs statin groups will be compared and evaluated for significant differences

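### SAP 1 puts quality of life in the between-arm aim, but SAP 6.2 prespecifies no between-arm comparison of DLQI or RAND36: its repeated measures ANOVA names no factors

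*SAP*

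**What the plan says.** **The aim.** The SAP Introduction (Section 1) asks whether the combination "can reduce the severity (size, color, quality of life impact) of disseminated superficial actinic vs statin therapy alone". Quality of life is therefore one of three named components of a comparative question. SAP Section 3 repeats it in Aim 1, "To evaluate the response (lesion size, color, patient quality of life) to treatment with topical cholesterol/lovastatin and lovastatin alone", and gives it an aim of its own, Aim 3: "Access quality of life outcomes through RAND36 and DLQI surveys". Protocol Section 4.0 lists it as an endpoint: "Validated scale changes: Patient Quality of Life (RAND36, DLQI").

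**The analysis.** The quality-of-life paragraph of SAP 6.2 has three parts:
- a baseline cross-sectional part, in which "self-reported DSAP-related impact on QoL (scale 1-10) was averaged at baseline";
- visit summaries, in which "the RAND36 and Dermatology Life Quality Index (DLQI) were distributed and averaged at weeks 0, 4, 8, and 12";
- one sentence on methods: "Statistical measures used in analysis included a Repeated Measures Analyses of Variance (ANOVA) and Pearson correlation coefficient".

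**The other outcomes.** For the photograph score, SAP 6.1 is explicit: "Overall efficacy will be examined using a 2X4 (Drug X Time) Repeated Measures Analyses of Variance (ANOVA"), followed by a statement that the two drug groups will be compared. The first sentence of SAP 6.2 sets a chi-square test across drug at the final visit for self-reported satisfaction.

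**The concern.** The SAP names the drug contrast for the outcomes before and beside quality of life, and then leaves it out for DLQI and RAND36. It also leaves out the time point of interest, the RAND36 scores to be used, the estimate to be reported and the analysis population.

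Two analysts could follow SAP 6.2 faithfully, one testing change over time in all patients together and the other testing drug by time, and answer different questions. Only the second addresses the Introduction's aim. A significant time effect from the first could be misread as support for adding cholesterol.

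Timing adds to the risk. The paragraph is in the past tense and SAP 2.1 already reports 31 patients enrolled. The documents do not say whether questionnaire results had been examined by arm, but a model left open at this stage can be chosen with the data in view.

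**Working it through.** The documents give no power, effect size, SD or precision figure for quality of life, so there is no stated figure to reproduce. The check is a comparison of texts, followed by illustrative arithmetic.

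**1. Is the drug contrast stated?**

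| Outcome | Place | Method | Drug contrast |
|---|---|---|---|
| DSAP-GASI | SAP 6.1 | 2 x 4 repeated measures ANOVA | Stated |
| Self-reported satisfaction | SAP 6.2, first paragraph | Chi-square, final visit | Stated |
| DLQI, RAND36 | SAP 6.2, second paragraph | Visit averages, repeated measures ANOVA, Pearson correlation | Not stated |

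No general rule fills the gap. The opening of SAP Section 6 bases treatment efficacy on photographs, so the 6.1 model does not carry over to questionnaires by default.

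**2. What would a time-only model show?** Let the mean changes be dA (cholesterol/lovastatin, 15 patients) and dB (lovastatin, 16 patients). The pooled change is (15 dA + 16 dB)/31. The aim concerns dA - dB. Many values of that difference give the same pooled change, and because both arms receive lovastatin the pooled change cannot be assigned to cholesterol.

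**3. Can the planned data answer the question?** Yes. Both questionnaires are given at weeks 0, 4, 8 and 12 in two randomised arms. With 31 patients, a drug-by-time ANOVA has 31 - 2 = 29 between-patient degrees of freedom, and its interaction test has 3 and 3 x 29 = 87.

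**4. How precise would the arm comparison be?** Inputs: 31 enrolled (SAP 2.1) and 50/50 assignment (Protocol 10.0). Assumptions: a 15/16 split, no dropout, and a baseline to week-12 correlation r of 0.5 to 0.7.

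- Unadjusted week-12 difference, 95% CI half-width: t(0.975, 29) x sqrt(1/15 + 1/16) = 2.045 x 0.359 = 0.735 SD.
- Baseline adjustment against unadjusted week-12 scores, SE factor sqrt(1 - r²): 0.866 at r = 0.5 and 0.714 at r = 0.7, a reduction of about 13% to 29%. The half-width becomes about 0.735 x 0.866 = 0.64 SD or 0.735 x 0.714 = 0.52 SD.
- Baseline adjustment against change scores, SE factor sqrt((1 + r)/2): 0.866 at r = 0.5 and 0.922 at r = 0.7, a reduction of about 13% and 8%.

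**5. What could be detected?** Assuming two-sided alpha 0.05 and 80% power, the detectable difference is (1.96 + 0.84) x 0.359 = 1.01 SD (1.04 SD using the t distribution). With baseline adjustment it is 0.87 SD at r = 0.5 and 0.72 SD at r = 0.7. Unadjusted power is about 29% for a true difference of 0.5 SD and about 61% for 0.8 SD. If only 12 or 10 patients per arm were analysable, the unadjusted detectable difference would rise to 1.14 or 1.25 SD.

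**The case against.** The strongest reply is that SAP 6.2 does name a repeated measures ANOVA, and the only such ANOVA the SAP defines is the drug-by-time model in 6.1. The questionnaires have the same four time points, so reading 6.2 as the same model is natural. This stands to the extent that drug is unstated, not excluded. It does not close the gap, because nothing in 6.2 refers back to 6.1.

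A reader might infer three stronger points, none of which the documents support:
- **That DLQI and RAND36 are analysed only as visit averages.** The sentence following the averages names the ANOVA and the Pearson correlation.
- **That the arms are pooled, so the trial cannot compare quality of life or has no power to.** Nothing says the arms are pooled, and the planned data allow the comparison.
- **That the 1-10 impact item is mishandled.** SAP 6.2 presents it as part of a baseline cross-sectional description, and SAP 4.2 does not list it separately as an outcome. It is already a baseline descriptor.

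It is also fair to say that not every aim is comparative. Aim 1 names both treatments without a contrast, Aim 3 has no between-arm wording, and the working hypothesis is that both treatments help. The comparative reading rests on the Introduction, which is nevertheless explicit.

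Finally, this is a secondary outcome in a trial of 31 patients, and any estimate will be imprecise. That lowers the severity. It is also a reason to settle on one estimate with its interval in advance.

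**Conclusion.** The concern holds as a failure to prespecify. Quality of life is a named component of the SAP's comparative aim, and SAP 6.2 does not commit to any between-arm comparison of DLQI or RAND36.

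Adding the word drug to the ANOVA would remove most of the ambiguity. It would still leave a 3-degree-of-freedom interaction test with no single week-12 estimate. A baseline-adjusted week-12 difference answers the aim directly and uses the baseline score already collected.

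Expected precision is a half-width of about 0.735 SD unadjusted, or roughly 0.52 to 0.64 SD adjusted. These figures rest on the assumed 15/16 split, no dropout and a correlation of 0.5 to 0.7, none of which the documents give. Severity is moderate.

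**What to change.** In SAP 6.2, replace the sentence on statistical measures for quality of life with text to this effect:

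- DLQI total and the RAND36 scale scores will be compared between randomised arms in a repeated-measures model with arm, visit, arm-by-visit and the baseline score as covariate; the outcome visits are weeks 4, 8 and 12.
- All randomised patients with available questionnaire data will be included, whether or not their photographs are usable. State this in SAP Section 7 as well, so that its general exclusion of missing data is not taken to drop patients who missed one questionnaire.
- The adjusted week-12 difference will be reported with its 95% CI. DLQI is the main quality-of-life measure; RAND36 scales and weeks 4 and 8 are supportive, with no multiplicity claims.

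If Pearson correlations are kept, name the variables and the visit. The 1-10 item needs no change. Date the revision and state whether questionnaire results by arm had been seen.

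The cost is SAP wording and one model per scale, with no new data. The downside is a little more analysis and an estimate that will be imprecise at this sample size.
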